6.4.4. Missing Data

Missing responses will be assumed to be missing completely at random. Analyses will include all samples available at each study time point.

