1. INTRODUCTION

Respiratory syncytial virus (RSV) causes upper and lower respiratory infections in children and adults of all ages, and leads to significant morbidity and mortality in pediatric, immunocompromised, and geriatric populations [1]. Worldwide, RSV is the leading cause of respiratory tract infections in children, infecting 50-70% of all children by age one and nearly all children by age two [2, 3]. About 2% of all children will require hospitalization for RSV. Infants born prematurely or those with congenital heart disease have a particularly high risk for severe disease, but more than half of hospitalized infants, have no identified risk factors. The peak age of hospitalization is between 2 and 3 months of age, but more than half of all hospitalizations in children under 5 years of age occur after 6 months [4-7].

Other risk factors include a family history or genetic predisposition to allergic inflammation and increase in IL-13 and IL-4 responses or a low level of maternally-transferred RSV-specific neutralizing activity [8]. Additionally, infants hospitalized for RSV are at greater risk for childhood wheezing and asthma. Adults with compromised immune systems and those ages 65 and older are also at increased risk of severe disease [9, 10].

Nearly all humans contract RSV by the age of three and then repeatedly throughout their lifetime [11, 12]. The economic impact of RSV in the United States (US) alone exceeds \$400 million per year [13, 14] and worldwide, annual RSV hospitalizations are estimated to number more than 3.4 million [15].

Currently, there is no licensed RSV vaccine. A single licensed antiviral therapy, Palivizumab (Synagis™), is currently available for prevention of RSV. Palivizumab is an anti-RSV fusion protein-specific monoclonal antibody (mAb) used as passive prophylaxis to reduce the frequency of severe RSV disease in premature infants, but is only recommended for infants born at 28 weeks of gestational age or less [16-20]. Target populations for an RSV vaccine include pregnant women, infants, young children, and the elderly. It is anticipated that age-specific vaccine strategies will be needed to generate effective immunity across a range of age groups [21].

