4.2.5. Follow-Up through End of Study

Study follow-up will continue via clinical visits through 44 weeks after the first study injection. The visit schedule is based on intervals of time after each study injection administration. Any subject who receives at least one study injection (including those subjects who elect not to

receive the optional second dose) will be expected to continue with follow-up for safety and immunogenicity through study Week 44 as per Schedule of Evaluations (Appendix III).

Throughout the study, any subject who is suspected of having an upper respiratory infection based on the presence of rhinorrhea in conjunction with at least one additional sign and/or symptom should be evaluated by nasal flock swab for PCR diagnostic purposes.

The schedule of visits, allowable windows for completing the visits, and evaluations performed at each visit are shown in the Schedule of Evaluations in Appendix III. After Day 0, deviations from the visit windows in completing study visits are discouraged and will be recorded as protocol deviations, but are permitted at the discretion of the PI.

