5. SAFETY AND ADVERSE EVENTS

5.1. Adverse Events

An adverse event (AE) is any untoward or unfavorable medical occurrence in a human subject, including any abnormal sign (e.g., abnormal physical exam or laboratory finding), symptom, or disease temporally associated with the use of study treatment, whether or not considered related to the study treatment.

AEs will be graded according to the Table for Grading Severity of AEs ([Appendix IV](#)). The following guidelines will be used to determine if an AE should be recorded in the database:

- Solicited AEs (i.e. reactogenicity parameters) will be recorded in the study database for 7 days after each study injection without the collection of product attribution assessments.

Clinicians will follow and collect resolution information for any reactogenicity symptoms that are not resolved within 7 days.

- Unsolicited AEs will be recorded in the study database from the date of receipt of each study injection through the visit scheduled at 28 days after each injection with the collection of product attribution assessments. At other time periods between injections and when greater than 28 days after the last injection, only SAEs (as detailed in [Section 5.2](#)) and new chronic medical conditions will be recorded as an AE through the last study visit.

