6. STATISTICAL CONSIDERATIONS AND SAMPLE ANALYSIS

6.1. Overview

This is a dose-escalation study to evaluate the safety and immunogenicity of a 2-dose regimen with the DS-Cav1 vaccine given alone or with adjuvant. As available, the effect of a 1-dose regimen will also be evaluated in up to 5 subjects in each group who will be offered the option to receive only a single administration of the study product. The primary objectives relate to safety and tolerability; the secondary and exploratory objectives relate to immunogenicity and durability of immune responses.

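### Section 6.4.4 makes no provision for samples taken after an RSV infection, so titres from Week 8 on can mix natural boosting with vaccine durability

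*Combined protocol and SAP*

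**What the plan says.** Section 6.4.4 consists of two sentences: "Missing responses will be assumed to be missing completely at random", and "Analyses will include all samples available at each study time point". Neither mentions infection. The other relevant places are these.

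- **Section 1** on reinfection: "Nearly all humans contract RSV by the age of three and then repeatedly throughout their lifetime".
- **Section 4.2.5** on follow-up: "Study follow-up will continue via clinical visits through 44 weeks after the first study injection". One-dose subjects are included. At any time in the study, a subject with a runny nose and at least one further sign or symptom "should be evaluated by nasal flock swab for PCR diagnostic purposes". No pathogen is named, and nothing is said about databasing the result or using it in an analysis.
- **Section 5.1** on adverse events outside the 28-day windows: "At other time periods between injections and when greater than 28 days after the last injection, only SAEs" and "new chronic medical conditions will be recorded as an AE through the last study visit".
- **Section 6.1** on aims: "the secondary and exploratory objectives relate to immunogenicity and durability of immune responses". Section 1.1 gives the duration of the response after the first dose as the reason for making the second dose optional.
- **Section 6.4.3**: the primary immunogenicity time points are 2 and/or 4 weeks after dose 1. Analysis cohorts are defined by vaccination status, with details left to a SAP whose text is not in the document supplied.
- **Table 1 and Section 6.1**: every group receives vaccine. Section 6.1 puts the one-dose subjects at up to 5 per group, but the Table 1 footnote also offers the option to additional subjects.
- **Appendix III**: serum is drawn at Weeks 8, 12, 13, 14, 16, 24, 36 and 44.

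**The concern.** An RSV infection raises neutralizing titre in the same direction as the vaccine. Once one has occurred, the subject's later samples no longer show the vaccine response alone. With no unvaccinated arm, natural boosting cannot be subtracted. Late titres would then be too high and waning would look slower than it is.

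An infection between Weeks 4 and 12 acts differently. It raises the pre-boost value, so the within-subject rise after the second dose (a comparison planned in Section 6.4.3) can look smaller.

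Contrasts are not equally exposed. Alum and no-alum groups at one dose level are randomized concurrently and should be roughly balanced. Dose levels open in sequence (Sections 4.3 and 6.4.6), and the one-dose option goes to the last subjects enrolled. Dose comparisons and one- versus two-dose comparisons can therefore cover different calendar periods, and Section 1.1 places the peak of RSV risk in winter.

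**Working it through.** **The plan's own figure.** The plan gives no figure for durability or for the one-dose subgroups. Its only immunogenicity figure is the power statement in Section 6.3.2: 90% for about 0.45 log10 with 15 per group and about 0.3 log10 with 30 per group, at SD 0.5. As a within-subject t-test (two-sided 0.05 assumed), the noncentralities are 0.45/(0.5/√15) = 3.49 and 0.3/(0.5/√30) = 3.29. These give power 0.899 and 0.888, so it reproduces in that form. As a two-sample t-test it does not (0.66 and 0.63), which is a separate matter. Only the SD is used below.

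**Inputs.** SD 0.5 log10, the conservative end of the 0.2-0.5 range in Section 6.3.2. n = 5 (one-dose subgroup, Section 6.1) and n = 15 (full group, Table 1). The boost size and infection rate are not in the documents. I assume a 2- to 10-fold boost and 2-20% of subjects infected by Week 44.

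**Sampling error.** SE = 0.5/√n, which is 0.224 at n = 5 and 0.129 at n = 15. The 95% half-widths are 2.776 × 0.224 = 0.62 and 2.145 × 0.129 = 0.28 log10.

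**Effect of one infected subject.** If the boost is B log10, the group mean shifts by B/n and the geometric mean titre is multiplied by 10^(B/n).

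| Assumed boost | B (log10) | n = 5: shift, ratio, in SE | n = 15: shift, ratio, in SE |
|---|---|---|---|
| 2-fold | 0.301 | 0.060, ×1.15, 0.27 | 0.020, ×1.05, 0.16 |
| 4-fold | 0.602 | 0.120, ×1.32, 0.54 | 0.040, ×1.10, 0.31 |
| 10-fold | 1.000 | 0.200, ×1.58, 0.89 | 0.067, ×1.17, 0.52 |

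At SD 0.2 the half-width at n = 5 is 2.776 × 0.2/√5 = 0.25, so even the largest shift (0.20) stays inside it, though only just.

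**Chance of at least one infection by Week 44**, 1 − (1 − p)^n:

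| p | n = 5 | n = 15 |
|---|---|---|
| 2% | 10% | 26% |
| 5% | 23% | 54% |
| 10% | 41% | 79% |
| 20% | 67% | 96% |

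These are cumulative to the last visit and are lower at earlier ones.

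**Expected bias.** On average the mean shifts by p × B, whatever n is: from 0.02 × 0.301 = 0.006 to 0.20 × 1.0 = 0.20 log10, and 0.05 log10 at 5% and 10-fold.

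**The case against.** Several points on the other side stand.

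- Section 6.4.4 is an available-case statement under Missing Data. A reader might infer that the plan has decided to count infected subjects' samples as vaccine response. It has not: it is silent on infection. The SAP may add a rule, although Section 6.4.3 ties its cohorts to vaccination status.
- The PCR in Section 4.2.5 is not described as RSV-specific.
- The listed secondary objectives (Section 3.2) are tied to 2 and/or 4 weeks after each injection, and no waning estimator is defined. The point therefore bears on later, mostly exploratory results.
- Boost size and infection rate are assumptions. Section 1.3 reports that subjects already show a more than 10-fold rise, and nothing in the documents supports a further large rise on infection.
- Infection results are not necessarily lost. Unsolicited adverse events are recorded for 28 days after each injection, and laboratory reports are source documents (Section 9.3.3). They would have to be retrieved rather than read from the database.
- Leaving out post-infection samples can introduce its own bias. Section 1.1 treats serum neutralizing activity as a correlate of protection, so infected subjects may tend to be low responders. Dropping their later samples would then also push late means up.

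The last point is the strongest. It decides the form of the remedy, but it does not remove the gap: the plan has no way to show how far late titres depend on infection.

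**Conclusion.** The gap is real and modest. Titres from Week 8 on, including the Week 12 pre-boost value and the one-dose results, can mix natural boosting with vaccine durability, and the plan neither databases the PCR results nor prespecifies a way to look at this. The Week 2 and Week 4 primary comparisons leave little time for infection and are little affected. Per infected subject, the distortion of the geometric mean is about 15-58% at n = 5 and 5-17% at n = 15, under an assumed 2- to 10-fold boost.

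Three stronger readings are tempting, and the documents do not support them. First, one infection does not dominate a one-dose subgroup: a shift of 0.06-0.20 log10 is at most 0.9 SE at SD 0.5, and imprecision is the larger problem there. Second, small subgroups are not more biased on average, since p × B does not depend on n; only the effect per infection is larger. Third, a near-certain infection somewhere among the one-dose subjects cannot be claimed. At n = 30 the formula gives 45% to over 99% for p of 2-20%, but that needs all 30 nominally eligible subjects to forgo the second dose, and Section 6.1 promises only an analysis as available. The footnote, for its part, allows more than 5 in a group.

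**What to change.** Enter the date, pathogen and result of each respiratory PCR in the study database through Week 44. In Section 6.4.4 or the SAP, prespecify that Week 8-onward results and one-dose results are reported twice: once with all samples, and once leaving out samples taken after a PCR-confirmed RSV infection while keeping that subject's earlier samples. Which of the two is the main analysis can be left to the trial team, but it should be named in advance so that the choice is not made after high late titres have been seen in very small subgroups.

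This is a cheap improvement. The swabs are already required, so it costs a small addition to the database and one extra analysis. Two limits remain. Unswabbed or asymptomatic infections are still missed, and the exclusion analysis may selectively drop low responders, so the two sets of results should be read together.

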6.4.5. Interim Analyses

An interim analysis of immunogenicity data may be performed when at least 10 subjects from Groups 1-4 reach 4 weeks post first dose. Reports will be provided to the PI and other key VRC investigators for the purpose of informing future trial-related decisions in a timely manner and may be published as preliminary data. Results should in no way influence the conduct of the trial in terms of early termination or later safety or immunogenicity endpoint assessments.

6.4.6. Randomization of Treatment Assignments

At the start of the study, subjects will be randomized 1:1 to Groups 1 and 2. If the criteria for the first Dose Escalation are met, procedures for the interim safety review are completed, and there are at least 10 people enrolled in each of Groups 1 and 2, subjects will be randomized 1:1 in Groups 3 and 4. If the criteria for the second Dose Escalation are met, procedures for the interim safety review are completed, and there are at least 10 people enrolled in each of Groups 3 and 4, subjects will be randomized 1:1 in Groups 5 and 6. Once all groups have at least 10 subjects per group, or if the dose escalation criteria are not met, subjects will be randomized in equal proportions to all groups that are open.

The subject and the study clinicians will be informed of the subject's group assignment upon completing the enrollment in the database.

To decrease the potential for participant dropouts during the period between randomization and initial vaccination, randomization will occur on Day 0 after the study consent is signed and eligibility is confirmed. If subjects accrued to a study group do not complete the number of injections and/or a follow-up duration specified, then additional subjects may be accrued in that group.

7. PHARMACY PROCEDURES

7.1. Study Products

The study products are prepared under cGMP by the VRC Pilot Plant and must meet lot release specifications prior to clinical use. This study includes one investigational vaccine, one adjuvant, and one diluent as follows:

- VRC-RSVRGP084-00-VP (DS-Cav1) drug product is a sterile, aqueous, buffered solution filled under aseptic conditions into single dose vials at a concentration of 500 mcg/mL. The formulation buffer is comprised of 20mM Histidine (buffer), 100mM Potassium Chloride (isotonic acid), 100mM Arginine HCl (stabilizer) and 2.5% weight per volume Sucrose (stabilizer) at pH 6.5. The drug product is aseptically filled at a volume of 1.2 ± 0.10 mL in a 3 mL glass vial. Vials contain a clear to slightly hazy sterile solution; some small white translucent particles may be visible.
- Aluminum Hydroxide Suspension, alum, adjuvant is composed of Alhydrogel[®] 2% (Brenntag Biosector, Frederikssund Denmark) diluted with water for injection to a concentration of 5 mg/mL. Adjuvant is aseptically filled at a volume of 0.7 ± 0.1 mL.
- VRC-PBSPLA043-00-VP, diluent, is comprised of Phosphate Buffered Saline (PBS) aseptically filled into single dose vials at a volume of 1.2 ± 0.10 mL.

7.2. Study Product Presentation and Storage

7.2.1. Labels

At the time of study product delivery to the pharmacy, study products labels will have specific product information (e.g., lot number, fill volume, storage temperature). Labels will contain an Investigational Use Statement (“Limited by Federal Law to Investigational Use”) and manufacturer information.

7.2.2. Storage

VRC-RSVRGP084-00-VP: DS-Cav1 vaccine vials will be shipped within the recommended temperature range using appropriate shipping configurations, to the study pharmacist or designee. Vials of vaccine should be stored until use at -35°C to -15°C in a qualified, continuously monitored, non-frost-free freezer until use. As freezer temperatures may fluctuate, a temperature range of -45°C to -10°C is acceptable. Storage below -45°C is not permitted because of the stopper limitation.

Vials, intended for single use only, do not contain preservative and should not be refrozen after thaw. Vaccine vials are removed from the freezer and equilibrated to room temperature prior to product administration.

Aluminum Hydroxide Suspension: Vials of alum are stored until use at 2°C to 8°C in a qualified, continuously monitored refrigerator. Do not freeze. Vials of adjuvant are intended for single use only.

VRC-PBSPLA043-00-VP: Vials of PBS are stored until use between -45°C to -10°C in a qualified, continuously monitored, non-frost-free freezer. Vials of diluent are intended for single use only and should not be refrozen after thawing.

7.2.2.1. Deviations in Temperatures

Temperature excursions that are outside of the specified ranges will be reported per pharmacy guidelines. If deviations in storage temperature occur from the normal allowance, the site pharmacist or designee must report the storage temperature excursion promptly to the PI and IND Sponsor and product must be quarantined in a separate area. The excursion must be

evaluated and investigated and action must be taken to restore and maintain the desired temperature limits. Pending the outcome of the investigation, the IND Sponsor will notify the pharmacist or designee if continued clinical use of the product is acceptable.

7.3. Preparation of Study Products for Administration

Refer to the group assignment for the study subject. The pharmacy will label the syringe before delivery to the clinic with the subject identifier, the date, and the time allowance for administration.

The following general instructions apply to all vaccine dose preparations (alone and with adjuvant) for injection.

- Preparation will be done by a Pharmacist or designee in a clean preparation unit with limited access;
- Prepare all doses under sterile conditions;
- Thaw the vial(s) containing VRC-RSVRGP084-00-VP and VRC-PBSPLA043-00-VP at ambient temperature (15°C to 25°C);
- The vaccine (alone and with adjuvant) is stable in the vial and syringe for 8 hours refrigerated or at room temperature following removal from recommended storage conditions;
- Administer within 8 hours following removal of vaccine from freezer;
- Keep the prepared syringe at room temperature and out of direct sunlight;
- Inversion of a prepared vial or syringe is defined as a gentle, complete 180 degree rotation of the container.

7.3.1. Preparation of VRC-RSVRGP084-00-VP (non-adjuvanted)

- For 500 mcg dose: withdraw 1.0 mL (500 mcg) into a syringe for administration.
- For 150 mcg dose:
 - Transfer 0.45 mL (225 mcg) of vaccine into a new sterile vial using a syringe,
 - Transfer 1.05 mL of PBS diluent into the same vial. (Total preparation volume = 1.5 mL),
 - Invert vial 5x to mix,
 - Withdraw 1.0 mL (150 mcg) into a new syringe for administration.
- For 50 mcg dose:
 - Transfer 0.15 mL (75 mcg) of vaccine into a new sterile vial using a syringe,
 - Transfer 1.35 mL of PBS diluent into the same vial (Total preparation volume = 1.5 mL),
 - Invert vial 5x to mix,
 - Withdraw 1.0 mL (50 mcg) into a new syringe for administration.

7.3.2. Preparation of VRC-RSVRGP084-00-VP with Adjuvant

Vials of alum and diluent will be provided for field mixing.

- For 500 mcg dose with adjuvant:
 - Add 0.12 mL of adjuvant directly to a new vial of VRC-RSVRGP084-00-VP (1.2 mL vaccine; total preparation volume = 1.32 mL),
 - Invert vial 5x to mix, incubate at ambient temperature (15°C to 25°C) for 15 minutes,
 - Withdraw 1.1 mL into a new syringe for administration,
 - Invert syringe 5x to mix,
 - If not administered immediately, invert syringe 5x to mix immediately prior to administration.
- For 150 mcg dose with adjuvant:
 - Transfer 0.45 mL (225 mcg) of vaccine into a new sterile vial using a syringe,
 - Transfer 0.15 mL of adjuvant into the same vial,
 - Invert vial 5x to mix, incubate at ambient temperature (15°C - 25°C) for 15 minutes,
 - Transfer 0.9 mL of PBS diluent into the same vial, invert 5x to mix. (Total preparation volume = 1.5 mL),
 - Withdraw 1.0 mL (150 mcg) into a new syringe for administration,
 - Invert syringe 5x to mix,
 - If not administered immediately, invert syringe 5x to mix immediately prior to administration.
- For 50 mcg dose with adjuvant:
 - Transfer 0.15 mL (75 mcg) of vaccine into a new sterile vial using a syringe,
 - Transfer 0.15 mL of adjuvant into the same vial,
 - Invert vial 5x to mix, incubate at ambient temperature (15°C to 25°C) for 15 minutes,
 - Transfer 1.2 mL of PBS diluent into the same vial, invert 5X to mix. (Total preparation volume = 1.5 mL),
 - Withdraw 1.0 mL (50 mcg) into a new syringe for administration,
 - Invert syringe 5x to mix,
 - If not administered immediately, invert 5x to mix immediately prior to administration.

7.4. Study Product Administration

Injections must be administered within the time allowance on the syringe label using standard needle and syringe injection technique. The study product will be administered IM into the deltoid muscle by needle and syringe.

The plan for injection administration is to use standard injection techniques as follows:

- Group 1: Administer one injection of 1.0 mL of the 50 mcg/mL preparation for each 50 mcg non-adjuvanted dose;
- Group 2: Administer one injection of 1.0 mL of the 50 mcg/mL field mixed with alum for each 50 mcg dose;
- Group 3: Administer one injection of 1.0 mL of the 150 mcg/mL preparation for each 150 mcg non-adjuvanted dose;
- Group 4: Administer one injection of 1.0 mL of the 150 mcg/mL field mixed with alum for each adjuvanted 150 mcg dose;
- Group 5: Administer one injection of 1.0 mL of the 500 mcg/mL preparation for each non-adjuvanted 500 mcg dose;
- Group 6: Administer one injection of 1.1 mL of the 500 mcg/mL field mixed with alum for each adjuvanted 500 mcg dose.

